3.10 Definition of Lost to Follow-up

Subjects who cannot be contacted on or before the Week 26 visit during the treatment period and who do not have a known reason for discontinuation (eg, withdrew consent or AE) will be classified as “lost to follow-up” as the reason for discontinuation. The site will make three attempts to contact the subject by telephone and in the event the site is unable to reach the subject by telephone, the site will attempt to contact the subject via certified mail or an alternative similar method where appropriate.

3.11 Subject Compliance

Responsible trial personnel will dispense the IMP (ie, brexpiprazole and ADTs). Accountability and compliance verification should be documented in the subject’s trial records. Subjects must be counseled on the importance of taking the IMP as directed at all trial visits. If poor compliance continues (eg, multiple missed doses resulting in less than 80% overall compliance at any point in the trial), discontinuation of the subject from the trial should be considered. Subjects who habitually miss visits or habitually attend visits outside of the protocol-defined visit window are also noncompliant and should be considered for discontinuation. The medical monitor should be contacted if the investigator is uncertain whether a subject’s lack of compliance merits discontinuation from the trial.

3.12 Protocol Deviations

This trial is intended to be conducted as described in this protocol. In the event of a significant deviation from the protocol due to an emergency, accident, or mistake (eg, violation of informed consent process, IMP dispensing or subject dosing error, subject enrolled in violation of eligibility criteria or concomitant medication criteria), the investigator or designee will contact the sponsor’s designee (medical monitor) at the earliest possible time by telephone. Investigator and sponsor (or sponsor’s designee) will come as quickly as possible to a joint decision regarding the subject’s continuation in the trial. This decision will be documented by the investigator and the designated medical monitor, and reviewed by the site monitor.

4 Restrictions

4.1 Prohibited Medications

Concomitant medications taken by subjects who are rolling over into Trial 331-10-238 from a prior double-blind phase 3 trials should be reviewed for the prohibited medications listed in [Table 4.1-1](#). Any subject taking a prohibited concomitant medication should not be enrolled in Trial 331-10-238.

Table 4.1-1 List of Medications Prohibited During the Trial

1.	All psychotropic agents including, but not limited to, the following: 
 a) Antipsychotics, including depot or long-acting injectable formulations b) Anticonvulsants c) Antidepressants other than the ADTs listed in Table 3.2.1.2-1 d) Mood stabilizers (ie, lithium) e) Benzodiazepines, except when used to manage treatment emergent AEs such as agitation and anxiety^a f) Hypnotics, including ramelteon and other non-benzodiazepine sleep aids, except for specific medications when used to manage treatment-emergent AEs related to insomnia^b g) Stimulants h) Opioid analgesics, unless permission is obtained from the medical monitor. Permission for opioid use may be considered for a documented and clinically appropriate indication (eg, episodic pain condition, tooth extraction) if prescribed at a medically appropriate dose and frequency. i) Nutritional supplements and non-prescription herbal preparations with CNS effects (eg, St. John's Wort, omega-3 fatty acids, kava extracts, GABA supplements, etc)
2.	Investigational agents
3.	CYP2D6 inhibitors or CYP3A4 inhibitors and inducers. Selected CYP2D6 inhibitors ^c are: celecoxib, hydroxyzine, chloroquine, methadone, chlorpheniramine, moclobemide, clemastine, clomipramine, pyrilamine, diphenhydramine, quinidine, terbinafine, halofantrine, tripeleannamine. Selected CYP3A4 inhibitors are: amiodarone, fluvoxamine, amprenavir, indinavir, aprepitant, itraconazole, chloramphenicol, ketoconazole, cimetidine, nefazodone, clarithromycin, nelfinavir, clotrimazole (if used orally), quinupristin/dalfopristin, delavirdine, ritonavir, diltiazem, saquinavir, erythromycin, troleandomycin, fluconazole, verapamil. Selected CYP3A4 inducers are: carbamazepine, oxcarbazepine, phenytoin, dexamethasone, primidone, efavirenz, rifampin, nevirapine, St. John's Wort, phenobarbital, troglitazone. The medical monitor should be consulted for any questions regarding the potential for pharmacokinetic interactions with concomitant medications used by subjects during the trial.
4.	Barbiturates, except for the treatment of migraine headaches, provided that in the opinion of the investigator the dosing is medically appropriate.

GABA = gamma-aminobutyric acid.

^a Administration of specific oral benzodiazepines is permitted for the short-term management of treatment emergent AEs such as anxiety and agitation up to a maximum of 6 mg/day lorazepam (or equivalent) in divided doses. Short-acting benzodiazepines are to be used whenever possible. In countries where no short-acting benzodiazepines are commercially available, use of oral diazepam or clonazepam may be acceptable if prior authorization is obtained from the medical monitor. The following guide should be used to determine approximate lorazepam equivalents: 1 mg lorazepam = 15 mg oxazepam = 0.5 mg alprazolam = 5 mg diazepam = 0.5 mg clonazepam. The prescribed benzodiazepine should be discontinued as soon as the AE for which it was initiated subsides, as per

the investigator's discretion to avoid any withdrawal effects. Benzodiazepines must not be administered within 12 hours prior to scheduled efficacy and safety assessments, including EPS scales. Investigators are encouraged to delay scale administration until 12 hours have elapsed, if at all possible. However, if delaying administration of efficacy and safety scales is not feasible, the scales should still be administered and the use of benzodiazepine documented, including a notation of the drug name, dose, and time of administration on the eCRF.

^bNon-benzodiazepine sleep aids (ie, zolpidem, zaleplon, zopiclone, and eszopiclone only) are permitted for the treatment of insomnia, but not on the same day as administration of a benzodiazepine, regardless of indication. For the non-benzodiazepine sleep aids, sites should only utilize one of the listed medications that are approved for this indication in their respective countries and the country-specific prescribing information is to be used to determine the maximum allowable daily dose for the treatment of insomnia. Non-benzodiazepine sleep aids must not be administered within 12 hours prior to scheduled efficacy and safety assessments, including EPS scales. Investigators are encouraged to delay scale administration until 12 hours have elapsed, if at all possible. However, if delaying administration of efficacy and safety scales is not feasible, the scales should still be administered and the use of the sleep aid documented, including a notation of the drug name, dose, and time of administration on the eCRF.

^cFluoxetine, paroxetine, and duloxetine are protocol-defined ADTs that are also CYP2D6 inhibitors. In order to limit the potential higher exposure of brexpiprazole when coadministered with such inhibitors, the upper limit of the therapeutic ADT dose is limited to 40 mg for fluoxetine, 50 mg for paroxetine CR, and 60 mg for duloxetine (see [Section 4.2.1](#)).

4.2 Other Restrictions

4.2.1 Restricted Therapies and Precautions

The subject's best medical interests should guide the investigator in the management of conditions that are pre-existing or that develop during the trial (intercurrent illness or AEs). The investigator should examine the acceptability of all concomitant medications not explicitly prohibited. In order to ensure that appropriate concomitant therapy is administered, it is essential that subjects be instructed not to take any medications (either self-administered non-prescription drugs or prescription therapy prescribed by another physician) without prior consultation with the investigator. In particular, the investigator should caution the subject about concomitant use of the following during the trial:

- Non-steroidal anti-inflammatory drugs, aspirin, or other drugs that interfere with coagulation since the combined use of psychotropic drugs that interfere with serotonin reuptake and these agents has been associated with an increased risk of upper gastrointestinal bleeding.³²
- Triptans (eg, sumatriptan, naratriptan, almotriptan, frovatriptan, rizatriptan, eletriptan, and zolmitriptan), linezolid, and methylene blue since there have been rare post-marketing reports of serotonin syndrome or serotonin syndrome-like reactions (eg, mental status changes, hyperreflexia, autonomic effects, lack of coordination, and diarrhea) following the concomitant use of SSRIs or SNRIs and these drugs.^{33,34,35}

Electroconvulsive therapy was prohibited during the prior double-blind phase 3 trials and is also prohibited for the duration of Trial 331-10-238. Transcranial magnetic stimulation is also prohibited. In addition, subjects may not undergo implantation of a device for vagus nerve stimulation or deep brain stimulation during the trial.

Use of intramuscular benzodiazepines and continual use of oral benzodiazepines are prohibited throughout the trial. However, administration of specific oral benzodiazepines is permitted for the short-term management of treatment emergent AEs such as anxiety and agitation up to a maximum of 6 mg/day lorazepam (or equivalent) in divided doses. Short-acting benzodiazepines are to be used whenever possible. In countries where no short-acting benzodiazepines are commercially available, use of oral diazepam or clonazepam may be acceptable if prior authorization is obtained from the medical monitor. The following guide should be used to determine approximate lorazepam equivalents: 1 mg lorazepam = 15 mg oxazepam = 0.5 mg alprazolam = 5 mg diazepam = 0.5 mg clonazepam. The prescribed benzodiazepine should be discontinued as soon as the AE for which it was initiated subsides, as per the investigator's discretion to avoid any withdrawal effects.

Non-benzodiazepine sleep aids (ie, zolpidem, zaleplon, zopiclone, and eszopiclone only) are permitted for the treatment of insomnia, but not on the same day as administration of a benzodiazepine, regardless of indication. For the non-benzodiazepine sleep aids, sites should only utilize one of the listed medications that are approved for this indication in their respective countries and the country-specific prescribing information is to be used to determine the maximum allowable daily dose for the treatment of insomnia.

Anticholinergics are permitted for the treatment of EPS up to a maximum of 4 mg/day benztrapine or its equivalent and propranolol is permitted for akathisia or tremor up to a maximum of 20 mg three times daily (total of 60 mg/day). Sites should only utilize medications that are approved for these indications in their respective countries.

Benzodiazepines, non-benzodiazepine sleep aids, anticholinergics, and propranolol must not be administered within 12 hours prior to scheduled efficacy and safety assessments, including EPS scales. Investigators are encouraged to delay scale administration until 12 hours have elapsed, if at all possible. However, if delaying administration of efficacy and safety scales is not feasible, the scales should still be administered and the use of the medication documented, including a notation of the drug name, dose, and time of administration on the eCRF.

Fluoxetine, paroxetine, and duloxetine are protocol-defined ADTs in this trial; however, they are also CYP2D6 inhibitors. Data from Trial 331-08-207 and Trial 331-08-208 indicate that coadministration of CYP2D6 inhibitors with brexpiprazole can cause potentially higher plasma concentrations of brexpiprazole (up to 2-fold). In order to limit the potential higher exposure of brexpiprazole when coadministered with such inhibitors, the upper limit of the therapeutic ADT dose is limited to 40 mg for fluoxetine, 50 mg for paroxetine CR, and 60 mg for duloxetine. The investigator should consider the potential for higher brexpiprazole plasma concentrations when adjusting the dose of brexpiprazole for subjects who are receiving fluoxetine, paroxetine CR, or duloxetine as the assigned ADT.

All trial personnel should be familiar with the content of the Investigator Brochure for brexpiprazole in order to manage the subject's condition adequately and select appropriate concomitant medications, if needed.

4.2.2 Non-therapy Precautions and Restrictions

4.2.2.1 Precautions

Subjects should not undergo any elective medical procedure without prior consultation with the investigator. An elective procedure (minor surgery, dental surgery, orthopedic surgery, etc) that might require hospitalization or general anesthesia should be deferred until after the trial whenever clinically appropriate.

4.2.2.2 Restrictions

Subjects may only receive psychotherapy (eg, individual, group, marriage, or family therapy) if they initiated the therapy at least 42 days before enrollment in the prior double-blind phase 3 trial, participated in the therapy regularly during the prior double-blind phase 3 trial, and commit to maintain their participation during the course of Trial 331-10-238, or unless permission is obtained from the medical monitor.

Consumption of grapefruit, grapefruit products, Seville oranges, or Seville orange products within 72 hours prior to dosing and during the trial is prohibited. Subjects will be instructed to refrain from drinking alcoholic beverages or using illicit drugs during participation in the trial. The investigator may request a blood or urine drug screen at any time during the trial if there is a suspicion of illicit drug use.

5 Reporting of Adverse Events

5.1 Definitions

An AE is defined as any untoward medical occurrence associated with the use of a drug in humans, whether or not considered drug related.

A suspected adverse reaction means any AE for which there is a reasonable possibility that the drug caused the AE. For the purpose of IND safety reporting, "reasonable possibility" means there is evidence to suggest a causal relationship between the drug and the AE. Suspected adverse reaction implies a lesser degree of certainty about causality than adverse reaction, which means any AE caused by a drug.

A serious adverse event (SAE) includes any event that results in any of the following outcomes:

- death
- life-threatening, ie, the subject was, in the opinion of the investigator or the sponsor, at immediate risk of death from the event as it occurred. It does not include an event that, had it occurred in a more severe form, might have caused death.
- persistent or significant incapacity or substantial disruption of the ability to conduct normal life functions.
- requires in-patient hospitalization or prolongs an existing hospitalization
NOTE: A pre-scheduled hospitalization is not considered an SAE; however, SAE forms must be completed for all other hospitalizations, including hospitalization for psychiatric reasons. Psychosocial hospitalizations (eg, homelessness or need for shelter that is unrelated to the subject's underlying psychiatric condition) should not be reported as SAEs.
- congenital anomaly/birth defect
- other medically significant events that, based upon appropriate medical judgment, may jeopardize the subject and may require medical or surgical intervention to prevent one of the outcomes listed above, eg, allergic bronchospasm requiring intensive treatment in an emergency room or home, blood dyscrasias or convulsions that do not result in hospitalization, or the development of drug dependency or drug abuse.

Non-serious adverse events are all AEs that do not meet the criteria for a "serious" AE.

If a subject is experiencing an extrapyramidal symptom, the specific extrapyramidal symptom must be indicated on the AE page of the eCRF. Examples of AEs that are considered extrapyramidal symptoms include, but are not limited to: generalized rigidity,

hyperkinesia, dyskinesia, bradykinesia, akinesia, dystonia, hypertonia, akathisia, tremor, flexed posture, involuntary muscle contractions, athetosis, and chorea. If a subject is experiencing two or more of these symptoms, whether or not treatment with an anticholinergic is required, this is considered as extrapyramidal syndrome and must be entered as “extrapyramidal syndrome” on the AE page of the eCRF instead of the individual symptoms. Permitted treatments for EPS are described in [Section 4.2.1](#).

Immediately Reportable Event (IRE):

- Any SAE
- Any AE that necessitates discontinuation of IMP.
- Potential Hy's Law cases (any increase of AST or ALT \geq 3 times the upper normal limit with an increase in total bilirubin \geq 2 times the upper normal limit).
- Pregnancies are also defined as IREs. Although normal pregnancy is not an AE, it will mandate IMP discontinuation and must be reported on an IRE form to INC Research. Pregnancy will only be documented on the AE eCRF if there is an abnormality or complication.

Clinical Laboratory Changes: It is the investigator's responsibility to review the results of all laboratory tests as they become available. This review will be documented by the investigator's dated signature on the laboratory report. For each abnormal laboratory test result, the investigator needs to ascertain if this is an abnormal (ie, clinically significant) change from baseline for that individual subject. (This determination, however, does not necessarily need to be made the first time an abnormal value is observed. The investigator may repeat the laboratory test or request additional tests to verify the results of the original laboratory tests). If this laboratory value is determined by the investigator to be an abnormal change from baseline for that subject, this is considered an AE.

Severity: Adverse events will be graded on a 3-point scale and reported as indicated on the eCRF. The intensity of an adverse experience is defined as follows:

1 = Mild: Discomfort noticed, but no disruption to daily activity.

2 = Moderate: Discomfort sufficient to reduce or affect normal daily activity.

3 = Severe: Inability to work or perform normal daily activity.

IMP Causality: Assessment of causal relationship of an AE to the use of the IMP is defined as follows:

Related: There is a reasonable possibility of a causal relationship.

Possibly related: There is a reasonable causal relationship between the IMP and the AE. Dechallenge is lacking or unclear.

Unlikely related: There is a temporal relationship to IMP administration, but there is not a reasonable causal relationship between the IMP and the AE.

Not Related: There is no temporal or reasonable relationship to the IMP administration.

Investigators will assess IMP causality based on brexpiprazole.

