9.1 Adverse Events

All AEs will be coded by Medical Dictionary for Regulatory Activities (MedDRA) system organ class and preferred term. The incidence of the following events will be summarized:

- TEAEs by severity
- Potentially drug-related TEAEs
- TEAEs with an outcome of death
- Serious TEAEs
- Discontinuations due to TEAEs

A TEAE is defined as an AE that starts after the first dose of IMP or an AE that is reported at baseline and increases in intensity or becomes serious or trial drug-related or results in death, discontinuation, interruption or reduction of IMP.

In addition, incidence of TEAE during Treatment Phase of at least 5% by SOC and PT will be provided.

Incidence of TEAEs by SOC and PT will be summarized for sex, race and age subgroups.

EPS-related AEs will be grouped into five categories.

- 1) Dystonic Events, which include cervical spasm, dystonia, emprosthotonus, muscle contractions involuntary, muscle rigidity, muscle spasms, muscle spasticity, myotonia, nuchal rigidity, oculogyration, opisthotonus, pleurothotonus, risus sardonicus, torticollis, and trismus;
- 2) Parkinsonian Events, which include akinesia, asterixis, athetosis, bradykinesia, cogwheel rigidity, essential tremor, extrapyramidal disorder, freezing phenomenon, gait festinating, hypertonia, hypokinesia, hypokinesia neonatal, intention tremor, masked facies, parkinson's disease, parkinsonian crisis, parkinsonian gait, parkinsonian rest tremor, parkinsonism, tremor, and tremor neonatal;
- 3) Akathisia Events, which include akathisia, hyperkinesia, and psychomotor hyperactivity;
- 4) Dyskinetic Events, which include ballismus, buccoglossal syndrome, choreoathetosis, clumsiness, dyskinesia, dyskinesia neonatal, dyskinesia oesophageal, fumbling, nodding of head, on and off phenomenon, and tardive dyskinesia;
- 5) Residual Events, which include chorea, huntington's chorea, muscle twitching, and myoclonus.

Incidence of EPS-related TEAEs will be summarized by EPS category. This summary will also be provided by ADT.

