- CT-8.6.3.2 Incidence of Treatment-emergent Adverse Events Resulting in Discontinuation from Study Medication by System Organ Class, MedDRA Preferred Term and Severity – 52-Week Enrollers
- CT-8.6.3.3 Incidence of Treatment-emergent Adverse Events Resulting in Discontinuation from Study Medication by System Organ Class, MedDRA Preferred Term and Severity – 26-Week Enrollers
- CT-8.7.1 Incidence of TEAE Occurring in at Least 5 Percent of Patients by System Organ Class and MedDRA Preferred Term in the Total Group – All Subjects
- CT-8.7.2 Incidence of TEAE Occurring in at Least 5 Percent of Patients by System Organ Class and MedDRA Preferred Term in the Total Group – 52-Week Enrollers
- CT-8.7.3 Incidence of TEAE Occurring in at Least 5 Percent of Patients by System Organ Class and MedDRA Preferred Term in the Total Group – 26-Week Enrollers
- CT-8.8.1.1 Incidence of TE EPS-related AEs by EPS Category and MedDRA Preferred Term – All Subjects
- CT-8.8.1.2 Incidence of TE EPS-related AEs by EPS Category and MedDRA Preferred Term – 52-Week Enrollers
- CT-8.8.1.3 Incidence of TE EPS-related AEs by EPS Category and MedDRA Preferred Term – 26-Week Enrollers
- CT-8.8.2.1 Incidence of TE EPS-related AEs by EPS Category and MedDRA Preferred Term by ADT – All Subjects
- CT-8.8.2.2 Incidence of TE EPS-related AEs by EPS Category and MedDRA Preferred Term by ADT – 52-Week Enrollers
- CT-8.8.2.3 Incidence of TE EPS-related AEs by EPS Category and MedDRA Preferred Term by ADT – 26-Week Enrollers

CT-9.1 Listing of Deaths

CT-9.2.1 Listing of Serious Adverse Events – All Subjects

CT-9.2.2 Listing of Serious Adverse Events – 52-Week Enrollers

CT-9.2.3 Listing of Serious Adverse Events – 26-Week Enrollers

CT-9.3.1 Listing of Discontinuations from Study Medication Due to Adverse Events – All Subjects

CT-9.3.2 Listing of Discontinuations from Study Medication Due to Adverse Events – 52-Week Enrollers

CT-9.3.3 Listing of Discontinuations from Study Medication Due to Adverse Events – 26-Week Enrollers

CT-10.1.1.1 Mean Change from Baseline in Clinical Laboratory Test Results - Serum Chemistry – All Subjects

CT-10.1.1.2 Mean Change from Baseline in Clinical Laboratory Test Results - Serum Chemistry – 52-Week Enrollers

CT-10.1.1.3 Mean Change from Baseline in Clinical Laboratory Test Results - Serum Chemistry – 26-Week Enrollers

CT-10.1.2.1 Mean Change from Baseline in Clinical Laboratory Test Results - Hematology – All Subjects

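### Concurrent EPS symptoms are entered as one combined AE but analysed by symptom, so the Akathisia, Dystonic, Dyskinetic and Residual incidences are lower bounds, and where the combined entry is counted is not stated

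*Protocol*

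**What the plan says.** Protocol Section 5.1 has two recording rules for EPS adverse events. For one symptom, "the specific extrapyramidal symptom must be indicated on the AE page of the eCRF". The second rule opens "If a subject is experiencing two or more of these symptoms, whether or not treatment with an anticholinergic is required"; in that case *extrapyramidal syndrome* is entered "on the AE page of the eCRF instead of the individual symptoms". The section names 13 example symptoms, among them akathisia, dystonia, dyskinesia, chorea and tremor, and says the list is not exhaustive.

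SAP Section 9.1 codes each AE to a MedDRA system organ class and preferred term and groups EPS-related terms as Dystonic, Parkinsonian, Akathisia, Dyskinetic or Residual. "Incidence of EPS-related TEAEs will be summarized by EPS category", and again by antidepressant (ADT). Tables CT-8.8.1.x and CT-8.8.2.x (SAP Section 13) show category and preferred term. The one general extrapyramidal term is in the Parkinsonian list: "Parkinsonian Events, which include akinesia, asterixis, athetosis, bradykinesia, cogwheel rigidity, essential tremor, extrapyramidal disorder". The Residual list is "Residual Events, which include chorea, huntington's chorea, muscle twitching, and myoclonus".

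Separately, "incidence of TEAE during Treatment Phase of at least 5% by SOC and PT will be provided"; this is CT-8.7.x, titled "Incidence of TEAE Occurring in at Least 5 Percent of Patients".

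Neither document says how *extrapyramidal syndrome* is coded, which category it enters, or how its components are recovered.

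**The concern.** The recording rule removes the information that the analysis needs. The EPS table counts subjects by symptom type, while the AE page holds no symptom type for a subject with several symptoms at once. Those are the subjects whose EPS profile matters most.

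Frequency and severity of AEs is the primary outcome (Protocol Sections 3.5.1 and 7.1.3), and Protocol Section 1.3 lists akathisia among the most common TEAEs in the completed earlier trials. A reader of the EPS table would take the Akathisia row as the number of subjects with akathisia. Under the plan it is the number with akathisia recorded separately at least once. The same applies to dystonia, dyskinesia and chorea, and to the preferred-term lines in the other TEAE tables.

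**Working it through.** The plan gives no figure that depends on this point, so there is nothing to reproduce. The check is a comparison of the two texts, followed by conditional arithmetic.

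**1. Terms in SAP 9.1.** Dystonic 15, Parkinsonian 21, Akathisia 3, Dyskinetic 11, Residual 4: 15 + 21 + 3 + 11 + 4 = 54. *Extrapyramidal syndrome* is not among them. One term contains the word extrapyramidal: *extrapyramidal disorder*, under Parkinsonian Events.

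**2. Protocol symptoms mapped to SAP categories.** Of the 13 examples, 11 match a listed term.

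| SAP category | Protocol 5.1 symptoms | Count |
|---|---|---|
| Akathisia | akathisia, hyperkinesia | 2 |
| Dystonic | dystonia, involuntary muscle contractions | 2 |
| Dyskinetic | dyskinesia | 1 |
| Residual | chorea | 1 |
| Parkinsonian | akinesia, bradykinesia, hypertonia, tremor, athetosis | 5 |

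Generalized rigidity and flexed posture have no exact match. Each of the four non-Parkinsonian categories holds at least one symptom that the combined entry can absorb, and none holds a combined term.

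**3. One subject traced through.** A subject has akathisia and dystonia together, and neither is ever recorded alone. The AE page shows only *extrapyramidal syndrome*. The subject is absent from the Akathisia and Dystonic rows. If the entry codes to *extrapyramidal disorder*, the subject is counted as Parkinsonian; if it codes to no listed term, the subject is absent from the EPS table. A subject whose akathisia is also recorded alone at another time is still counted. The rule can therefore lower these four incidences and cannot raise them.

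**4. Possible pairs.** The 11 matched symptoms give 11 × 10 / 2 = 55 pairs.
- Both Parkinsonian: 5 × 4 / 2 = 10, so 55 − 10 = 45 pairs lose at least one symptom from another category.
- Neither Parkinsonian: 6 × 5 / 2 = 15. These become false Parkinsonian counts if the entry codes to *extrapyramidal disorder*. In the other 40 a Parkinsonian count is not false.

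These are possible combinations, not expected frequencies.

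**5. Tipping point for the 5% table (assumptions only).** Let r be the true percentage of subjects with akathisia, and u the share of them recorded only in combination. Reported incidence = r × (1 − u), which falls below 5% when u > 1 − 5/r. Subjects per 1,000 that must be lost: more than 10 × (r − 5).

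| r (%) | u must exceed (%) | Lost per 1,000, more than |
|---|---|---|
| 5.5 | 9.1 | 5 |
| 6 | 16.7 | 10 |
| 7 | 28.6 | 20 |
| 8 | 37.5 | 30 |
| 10 | 50.0 | 50 |

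A rate just above 5% is easily lost; a rate of 8 to 10% is not.

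**6. A bound from the planned tables.** Every subject missing from a symptom row has at least one combined entry. If all such entries code to one preferred term, counted in C subjects, and the akathisia line shows A subjects, then the number with akathisia lies between A and A + C. C can be read from CT-8.8.x if the term is listed there, and otherwise from CT-8.2.2.1.x, which covers all TEAEs by preferred term.

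**The case against.** The combining rule is explicit and deliberate, and grouping concurrent EPS is a legitimate convention. That stands as a defence of grouping, but not of analysing by symptom what was recorded as a group. A flag derived by program would keep both.

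The rating scales give partial cover. Under Table 3.6-1, SAS and BARS are done at baseline and at all seven treatment visits, and the BARS item analysed is the global akathisia rating. This stands as a separate measure of akathisia and parkinsonism. But the tables listed in SAP Section 13 summarise the scales as mean change from baseline, which does not give the number of subjects with an event. AIMS, the dyskinesia scale, is done only at baseline, Week 14 and Week 26/ET.

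The planned preferred-term tables would expose the combined term and bound the loss, as step 6 shows. This also stands, provided the entries code to a single term. It limits the harm, but a reader who is not told what the term contains would not know to apply the bound.

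A reader might infer that Parkinsonian Events will be over-counted. The documents do not support that, because the coding is not stated; if the entry codes to no listed term, Parkinsonian Events is under-counted too. A reader might also infer that akathisia will drop out of the 5% table. Nothing shows that any combined record exists, both r and u are assumed, and the table is a descriptive display in a trial with no power basis (Protocol Section 7.2). A term below 5% still appears in CT-8.2.2.1.x.

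**Conclusion.** The mismatch is in the text of the two documents. If sites follow Protocol 5.1 and the SAP is run as written, the Akathisia, Dystonic, Dyskinetic and Residual incidences are lower bounds. Parkinsonian Events can err in either direction.

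The same loss can affect every preferred-term TEAE table: all TEAEs (CT-8.2.2.x), severity (CT-8.2.3.x), at least 5% (CT-8.7.x), drug-related (CT-8.3.2.x), serious (CT-8.5.2.x) and discontinuation (CT-8.6.2.x). It would be wrong to infer that overall safety counts are understated. A combined entry is still an AE, so the numbers of subjects with any TEAE, any SAE, death or discontinuation due to a TEAE are unchanged.

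The size is unknown, because no document gives the share of subjects recorded only in combination. The akathisia figure of 7.0% in Protocol Section 1.3 is a reported pooled rate from earlier trials in other populations and cannot serve as the true rate here. The direction for the four categories is certain if the rule is followed and any subject's symptom is recorded only in combination; the amount is not. The change is worth making because it is cheap and concerns the primary outcome.

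**What to change.** **In SAP Section 9.1 and the table list:**
- State the preferred term to which *extrapyramidal syndrome* is coded.
- Show these records in their own combined/unspecified EPS row, outside Parkinsonian Events.
- Add a total for subjects with any EPS-related TEAE that includes them.
- Footnote CT-8.8.x and all preferred-term TEAE tables to say that symptom-level incidences are lower bounds because components of combined entries are not counted.

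**For records already entered:** query the components where source notes allow, and assign them to their categories. Protocol Sections 5.2 and 9.2 require AEs to be documented in source but do not guarantee that each component was written down, so some records will stay in the combined row.

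**If AE collection is still open:** change Protocol Section 5.1 so that each symptom is its own AE with onset and severity, and derive the combined status by program. This is probably too late. The SAP was approved in May 2017, and the protocol, issued in May 2011, estimated about 57 months from first enrolment to last completion. The SAP changes do not depend on it.

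**Cost:** a few lines of SAP text, one row, one total and a footnote; some queries, whose number the documents do not show; and, if the protocol changes, an eCRF guideline update and a few more AE lines per affected subject. A mid-trial change would put two recording rules in one dataset, which the tables should flag.
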